### 3 OBJECTIVES

#### 3.1 Primary Objective

Can neuro-navigated Transcranial Magnetic Stimulation be used as an additional outcome measure to EM-SCI assessments in a Spinal cord injury trial?

- Compare EM-SCI assessment with nTMS in ten chronic thoracic SCI patients
- Compare EM-SCI assessment with nTMS in ten chronic cervical SCI patients

#### 3.2 Secondary Objectives

nTMS stimulation combined with MRI Tractography can be used as an adjunct outcome tool with EM-SCI assessments for a planned first in human SCI gene therapy trial.

Specifically, nTMS will demonstrate sensitivity for cortico-spinal tract function, giving a novel tool for stratifying and selecting patients for SCI trials.

### 4 STUDY DESIGN

This is a pilot study in the assessment of nTMS as an adjunct tool in measuring outcome within chronic spinal cord injury patients. Initial PPI events will be performed where patients will be engaged in obtaining feedback on study design and protocol for both the pilot nTMS study and the potential subsequent Gene therapy trial. Following these events, suitable patients who meet the inclusion criteria and have displayed interest in participation will be consented for the study. Patients will then attend for a single day of assessments as follows:

1 - The International Standards for Neurological Classification of Spinal Cord Injury (ISNCSCI). The International Standards for Neurological Classification of Spinal Cord Injury (ISNCSCI) assessment protocol consists of two sensory examinations, a motor examination, and a classification framework (the impairment scale) to quantify the severity of the spinal cord injury. The grading is from A to E, with A being a complete injury with no motor or sensory function and E being normal sensory function. Patients recruited will vary between A and D to give an indication of variability in the motor response to allow comparisons between injury severity.

2 – Neurophysiology. Three standard neurophysiological measures will be registered: MEP (motor evoked potentials), SSEP (somatosensory evoked potentials) and NCV (nerve conduction velocity). MEPs and SSEPs of the tibialis and ulnar nerves quantify the status of the efferent and afferent pathways in the spinal cord. The NCV will be used to exclude peripheral nerve lesions.

3 – Functional Tests. Assessment of the walking ability of patients with movement disorders is an important outcome measure in rehabilitation. The Walking Index for Spinal Cord Injury II (WISCI II) has been validated in SCI patients, The WISCI II has an original scale that quantifies a patient's walking ability; a score of 0 indicates that a patient cannot stand and walk and the highest score of 20 is assigned if a patient can walk more than 10m without walking aids of assistance. In addition, the following two time tests will be performed: Timed Up & Go (TUG) test and 10-metre walking test (10MWT).

4 - Spinal Cord Independence Measure 3 (SCIM 3). The Spinal Cord Independence Measure (SCIM) is a disability scale developed specifically for patients with spinal cord lesions. It focuses on the requirement of personal assistance and/or technical aids with domains in self-care, respiration and sphincter management and mobility. The score is between 0 and 100.

[figure not shown]
5 - Graded and Redefined Assessment of Strength, Sensibility and Prehension version 1 (GRASSP v1). The GRASSP is an outcome measure to assess hand function in patients with a cervical spinal cord injury. It consists of three domains: 1. Strength, 2. Sensation and 3. Prehension: including relevant finger positioning performance with 6 Activities of Daily Living. The score is between 0 and 116.

6 - MRI Tractography followed by neuro-navigated Transcranial Magnetic Stimulation will be undertaken. The rationale is that nTMS will provide a more sensitive characterisation of a functional CST in SCI patients. Moreover, nTMS provides spatial resolution of the tracts which standard neurophysiology cannot determine. The addition of MRI tractography allows accurate neuro-navigated localisation of the CST and quantification of the fibre density of the CST.

After acquisition of the MRI scans, nTMS-seeded tractography will be performed. nTMS positive motor responses will be used as regions of interest and another region of interest will be placed in the brainstem at the level of the superior cerebellar peduncle. This technique will provide somatotopic tractography. DTI-derived metrics (Fractional Anisotropy (FA), Axial Diffusivity (AD), Radial Diffusivity (RD), Mean Diffusivity (MD) and Hindrance Modulated Orientation Anisotropy (HMOA)), number of fibres and volume will be calculated for both CSTs. Our hypothesis is that an abnormal cortical excitability will correlate with abnormal CST metrics supporting microstructure impairment. This may be particularly true with the tract specific metric, HMOA.

Comparisons between EM-SCI and nTMS/tractography assessments will be made to determine if nTMS can be used as an adjunct which is more sensitive in the assessment of SCI patients. For instance, nTMS can induce motor evoked potentials in patients with no active movement detected in neurological examination and this can have an impact in terms of prognostication of motor recovery, which is especially important for SCI trials.

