nTMS allows for an individual location of the magnetic stimulation within an acceptable margin of error derived from the registration process. When compared with non-navigated TMS, the navigated TMS allows for more spatially discrete cortical stimulation and more stable motor evoked potentials with significantly higher amplitudes and shorter latencies. Also, when different navigation methods are compared, 'E-field' navigation proved to be superior to line-navigation method. At King's, we use an E-Field nTMS. We combine nTMS with MRI tractography, a 3D modelling technique used to visually represent nerve tracts using data collected by diffusion MRI. This accurately delineates the location of the motor cortex. The advantage for this is pairing a positive TMS cortical response with a defined subcortical tract that carries that same motor information, thus confirming a true positive response.

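### The only cortical seed described for the corticospinal tract metrics is an nTMS-positive site, so a hemisphere without a response has no defined diffusion metrics

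*Protocol*

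**What the plan says.** Protocol section 4, item 6, describes nTMS-seeded tractography. The cortical region is defined by the nTMS result, and the second region lies in the brainstem at the superior cerebellar peduncle: "nTMS positive motor responses will be used as regions of interest and another region of interest will be placed in the brainstem". Five diffusion metrics (FA, AD, RD, MD, HMOA) are listed, and with them "number of fibres and volume will be calculated for both CSTs". No condition is attached and no other cortical seed is described.

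The metrics have three uses:

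- The mechanistic hypothesis in item 6: "Our hypothesis is that an abnormal cortical excitability will correlate with abnormal CST metrics supporting microstructure impairment".
- The comparison with standard assessments in item 6: "Comparisons between EM-SCI and nTMS/tractography assessments will be made to determine if nTMS can be used as an adjunct which is more sensitive".
- The secondary objective in section 3.2, which pairs nTMS with tractography as an adjunct outcome tool and adds: "Specifically, nTMS will demonstrate sensitivity for cortico-spinal tract function, giving a novel tool for stratifying and selecting patients for SCI trials".

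On enrolment, section 4, item 1 states: "Patients recruited will vary between A and D to give an indication of variability in the motor response". Section 5.1 asks for the ability to take part in the EM-SCI and nTMS assessments. It does not ask for a positive nTMS response.

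**The concern.** The seeding rule makes the availability of the tractography measure depend on the result of the tool under test. Where nTMS evokes no response there is no cortical region to seed from, although the MRI has been acquired. Every hemisphere with a CST metric is then nTMS-positive by construction.

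This fits the rationale in section 2, which is about "pairing a positive TMS cortical response with a defined subcortical tract that carries that same motor information, thus confirming a true positive response". It gives no information on negatives. Tractography could support a positive response, but it could not describe the tract in a hemisphere where nTMS found nothing.

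Two things are at stake. The comparison of tractography with EM-SCI would use a subset chosen by nTMS, although EM-SCI is planned for every participant. A study that hopes to stratify patients would also be unable to say whether responders and non-responders differ on any CST metric.

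**Working it through.** **What the text implies, step by step**

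1. Cortical seed: nTMS-positive sites only (section 4, item 6).
2. Promised output: metrics for both CSTs, that is 2 × 20 = 40 tracts in the 10 thoracic and 10 cervical participants of section 3.1.
3. Entry: grades A to D, no response required (section 5.1). A hemisphere with no positive site is therefore possible.
4. For such a hemisphere step 1 supplies no seed. FA, AD, RD, MD and HMOA have no tract to be averaged over. Fibre number and volume could be entered as zero, but no such convention is stated, and the zero would come from step 1 and not from the tract.
5. Steps 2 and 4 cannot both be met for that hemisphere.

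**How much it could cost**

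The protocol gives no non-response rate, effect size or power target, so there is no stated figure to reproduce. Everything below is an illustration.

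Assumptions: one CST metric and one EM-SCI measure, bivariate normal, true correlation 0.60, n = 20, two-sided 5% Pearson test, t = r√(m − 2)/√(1 − r²) with m participants left, 40,000 simulated studies. Participants without a tract are dropped.

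| Participants without a tract | Why they are lost | Mean r | Power |
|---|---|---|---|
| 0 | – | 0.59 | 84% |
| 4 | unrelated to the EM-SCI measure | 0.59 | 74% |
| 4 | non-response score correlates 0.5 with it | 0.57 | 69–70% |
| 4 | lowest on it | 0.49 | 53–54% |
| 10 | unrelated | 0.58 | 49% |
| 10 | score correlates 0.5 | 0.55 | 43% |
| 10 | lowest | 0.40 | 23% |

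Unrelated loss costs precision only. The correlation is attenuated when the loss tracks severity. With no non-response there is no loss.

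**Responder versus non-responder comparison**

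As written, no non-responding hemisphere has a diffusion metric, so the comparison cannot be made. If metrics existed for all 20 participants, the 95% interval half-width for a difference in means, in SD units, is t(0.975, 18) × √(1/a + 1/b), with t = 2.101:

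- 4 versus 16: 2.101 × √(0.25 + 0.0625) = 2.101 × 0.559 = 1.17 SD
- 10 versus 10: 2.101 × √0.2 = 2.101 × 0.447 = 0.94 SD

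Such a comparison is descriptive at this sample size.

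**The case against.** **Is a second reconstruction ruled out?** No. Item 6 opens by placing MRI tractography before nTMS, and tractography done first cannot be nTMS-seeded. A reader might infer that non-responding hemispheres are excluded from every tractography analysis. The protocol does not say so, and fibre number and volume could be scored zero. What stands is that the paragraph defining the metrics gives one seed and no fallback.

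**How often would it happen?** Unknown. One positive site from any mapped muscle provides a seed, half the sample is thoracic, and item 6 names no target muscles. If muscles supplied from above the lesion are mapped, the loss may be small. Losing 10 of 20 has no basis in the document and serves only as an outer case.

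**Would an anatomical seed show whether the CST is spared?** This is tempting but unsupported. The reconstructed tract ends in the brainstem, above any cervical or thoracic lesion. Section 4, item 2 assigns the state of the cord pathways to neurophysiology: "MEPs and SSEPs of the tibialis and ulnar nerves quantify the status of the efferent and afferent pathways in the spinal cord". An absent response is itself an nTMS result, available for everyone tested.

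**Would it rescue the excitability hypothesis?** Not for non-responders. An excitability value based on a response is missing for them as well, so that loss comes from nTMS and not from the seeding.

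**Does the seeding manufacture a correlation?** A reader might suspect this for fibre number and volume, if seed extent varies with the number of positive sites. The protocol does not say that it does, and nothing comparable is shown for the five diffusion metrics.

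**Is this preference, or a matter for the SAP?** nTMS seeding is a deliberate choice for somatotopic tracts and should stay. How a tract is generated, however, is a measurement rule that this protocol fixes. A later analysis plan cannot analyse a metric that was never produced.

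**Conclusion.** The point holds in a limited form. The seeding rule and the promise of metrics for both CSTs do not fit together for a hemisphere without an nTMS response, and the entry criteria allow such hemispheres. Where they occur, the tractography versus EM-SCI comparison and the tractography part of the secondary objective rest on hemispheres selected by the nTMS result, and no contrast of CST metrics by response is possible.

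The size cannot be fixed from the document. The power figures depend wholly on the assumed correlation, loss and dependence. This is a pilot study with no stated power, so none is missed. The primary comparison of nTMS with EM-SCI needs no tract and is unaffected. The point is worth correcting because the remedy is cheap and uses MRI already planned, not because a large loss has been demonstrated.

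**What to change.** In section 4, item 6, add text to this effect:

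*Both CSTs will also be reconstructed in every participant from the same MRI, using an anatomical precentral seed and the same brainstem region, processed without reference to the nTMS result. These metrics will be used to compare tractography with EM-SCI. The number of hemispheres without an nTMS response will be reported, and their intracranial CST metrics will be compared descriptively with those of responding hemispheres.*

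Keep the nTMS-seeded tracts as planned for somatotopy and for the excitability hypothesis, and report the anatomically seeded metrics alongside. State that the excitability correlation covers only hemispheres with a measured excitability value, and that the reconstructed tract does not assess the CST across the cord lesion.

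The cost is one extra processing run per participant and a few sentences, with no extra scan or visit. The added tracts are less somatotopically specific, which is why the nTMS-seeded ones are retained.

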## 5 CONSENT

The Informed Consent form must be approved by the REC and must be in compliance with GCP, local regulatory requirements and legal requirements. The investigator or designee must ensure that each trial participant, or his/her legally acceptable representative, is fully informed about the nature and objectives of the trial and possible risks associated with their participation. Participants reserve the right to withdraw consent at any point without reason.

Alternatively, recognising many centres have transitioned to virtual outpatient appointments and may not see a participant in person until the day of surgery, verbal informed consent can be obtained by telephone. This must be countersigned by a second investigator, to confirm that the individual received a verbal description of the study, had received the PIS, and had had sufficient time to consider the information and an opportunity to ask questions, and voluntarily agreed to participate in this study.

## ELIGIBILITY CRITERIA

### 5.1 Inclusion Criteria

- Single traumatic event at least 6 months prior to recruitment
- ISNCSCI grade A, B, C or D
- Able to participate in EM-SCI and nTMS assessments and capable of informed consent

### 5.2 Exclusion Criteria

- History of Malignancy
- History of other Neurological disease
- Pregnancy
- Other cord lesions or tethering
- Cord transaction or penetrating injury

## RECRUITMENT

Participants will be identified and recruited from spinal cord injury follow up clinics at King's College Hospital, where eligible patients will be approached. Patients will also be approached via Participant identification centres, with Stoke Mandeville Hospital (National spinal injuries unit) the agreed site for patient referrals.

## 6 PATIENT AND PUBLIC INVOLVEMENT (PPI)

Two Public Patient Involvement (PPI) events have taken place in the planning and preparation of this study. The first event took place in the National Spinal Injuries Centre at Stoke Mandeville (NSIC), England in November 2022. This was followed by an event in the National spinal injuries unit in Glasgow (February 2023).

Both involved presentations on Gene therapy as a novel treatment option for spinal cord injury and neuro navigated TMS as an assessment tool in chronic SCI. Participants were also consulted on the study design including the proposed full day of assessments planned.

Feedback from the PPI event's was overwhelmingly positive, with participants supportive of new studies that may further the management of SCI patients. Moreover no concerns were raised against the study design, and participants felt the full day of assessments was definitely feasible. All participants if eligible felt they would be interested in partaking within the neuro TMS trial despite any potential risks.

## 7 FUNDING AND SUPPLY OF EQUIPMENT

The study funding has been reviewed by the KCH R&I Office, and deemed sufficient to cover the requirements of the study.

The research costs for the study have been supported by AO Spine.

## 8 DATA HANDLING AND MANAGEMENT

Personal data will be obtained with full consent and transparency of its use. Confidentiality will be maintained through de-identification of participants.

Data will be made de-identifiable and stored in a secure university/hospital computer at King's College Hospital and King's College London, and only shared between accredited members of the direct care team via encrypted email. Personal data once no longer required will be erased in accordance with GDPR guidance, any remaining data/information will remain non-identifiable.

## 9 PEER AND REGULATORY REVIEW

The study will undergo initial peer review within the research team.

The study was deemed to require regulatory approval from the following bodies - HRA and REC. Each approval will be obtained before the study commences.

## 10 ADVERSE EVENTS AND INCIDENT REPORTING

### 10.1 Definitions of Adverse Events

| Term  | Definition   |
|---|--|
| Adverse Event (AE)  | Any untoward medical occurrence in a patient or study participant, which does not necessarily have a causal relationship with the intervention/treatment/procedure involved.   |
| Serious Adverse Event (SAE).  | Any adverse event that: 
 
• results in death,
 
• is life-threatening*,
 
• requires hospitalisation or prolongation of existing hospitalisation**,
 
• results in persistent or significant disability or incapacity, or
 
• consists of a congenital anomaly or birth defect
 
 |
| 
*A life- threatening event, this refers to an event in which the participant was at risk of death at the time of the event; it does not refer to an event which hypothetically might have caused death if it were more severe.
 
** Hospitalisation is defined as an in-patient admission, regardless of length of stay. Hospitalisation for pre-existing conditions, including elective procedures do not constitute an SAE.
 |  |

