### 10.2 Assessments of Adverse Events

Each adverse event will be assessed for severity, causality, seriousness and expectedness as described below.

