#### Severity

| Category | Definition   |
|----------|--|
| Mild     | The adverse event does not interfere with the participant's daily routine, and does not require further procedure; it causes slight discomfort                           |
| Moderate | The adverse event interferes with some aspects of the participant's routine, or requires further procedure, but is not damaging to health; it causes moderate discomfort |
| Severe   | The adverse event results in alteration, discomfort or disability which is clearly damaging to health  |

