### 10.3 Procedures for recording adverse events

- All adverse events will be recorded in the medical records in the first instance.
- All Adverse events will be recorded in the CRF following consent.
- All adverse events will be recorded with clinical symptoms and accompanied with a simple, brief description of the event, including dates as appropriate.
-

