## 10.4 Procedures for recording and reporting Serious Adverse Events

All serious adverse events will be recorded in the medical records and the CRF.

All SAEs (except those specified in section 16.2 as not requiring reporting to the Sponsor) must be recorded on a serious adverse event (SAE) form. The CI/PI or designated individual will complete an SAE form and the form will be emailed to the R&I Office ([[contact]](mailto:[contact])) within 1 working day of becoming aware of the event.

Where the event is unexpected and thought to be related to the intervention/treatment/procedure this must be reported by the Investigator to the REC and Health Research Authority, using the SAE Report form for non-CTIMPs (available from the HRA website) within 15 days.

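### The SAE definition has no medical-judgement criterion, so a severe, related, unexpected event treated without admission may need no report to the R&I Office, REC or HRA

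*Protocol*

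**What the plan says.** Protocol section 10.1 lists five ways for an adverse event to be serious: death, threat to life, hospitalisation or its prolongation, disability ("results in persistent or significant disability or incapacity"), and finally "consists of a congenital anomaly or birth defect". The list stops there. Two footnotes narrow it. On hospitalisation: "Hospitalisation is defined as an in-patient admission, regardless of length of stay". On threat to life: "it does not refer to an event which hypothetically might have caused death if it were more severe".

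Section 10.2 requires that "Each adverse event will be assessed for severity, causality, seriousness and expectedness as described below". The subsections that follow define severity, causality and expectedness only, so seriousness rests on the 10.1 list. The top severity grade reads: "The adverse event results in alteration, discomfort or disability which is clearly damaging to health".

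On handling, section 10.3 says "All Adverse events will be recorded in the CRF following consent", and it also requires an entry in the medical records. Section 10.4, headed for SAEs, says that these "must be recorded on a serious adverse event (SAE) form", to be emailed to the R&I Office within 1 working day. It adds a 15-day report to the REC and HRA when the event is unexpected and thought to be related.

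**The concern.** Every adverse event is graded for severity, causality and expectedness, but those grades do not by themselves send an event to the research-safety bodies. It must first be serious, and seriousness is a closed list that leaves the investigator no discretion.

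Participants come for one day of assessments that includes nTMS. An acute reaction during such a visit could be treated and settle without an in-patient admission. If it met no other criterion, it would need no SAE form and no REC or HRA report, even if graded Severe, Definitely related and Unexpected. The bodies overseeing the research would then have no required notice of a procedure-related event that they might want to consider before further participants are stimulated. The study's title presents it as a step towards a gene therapy trial, and the secondary objective proposes nTMS with tractography as an outcome tool there, so a complete safety record has value beyond these 20 participants.

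**Working it through.** No arithmetic applies. The check follows one defined event through every reporting route in sections 10 and 11.

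**The event.** It occurs at the study visit, is graded Severe, at least Probably related and Unexpected, is treated on site, and does not lead to admission.

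**Step 1: is it an SAE under 10.1?**
- Death and congenital anomaly: no.
- Hospitalisation: no, because there is no in-patient admission.
- Life-threatening: only if the participant was actually at risk of death at the time. A risk that might have arisen had the event been worse does not count.
- Disability: only if the disability or incapacity is persistent or significant. Persistence is not essential, so some events treated without admission will qualify here.

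If the last two are not met, the event is not an SAE, and no further criterion lets the investigator class it as one.

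**Step 2: which routes apply if it is not an SAE?**

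| Protocol section | Condition | Recipient | Required for this event? |
|---|---|---|---|
| 10.3 | any adverse event | medical records, CRF | Yes |
| 10.4, SAE form, 1 working day | SAE | R&I Office | No |
| 10.4, report within 15 days | unexpected and related | REC, HRA | No, on the natural reading |
| 10.6, notice within 3 days | urgent safety measures taken | REC, HRA, R&I Office | Only if such measures are taken |
| 10.7 | protocol violation | CI, R&I Office | No, unless there was also a breach |
| 10.8, DATIX | unintended or unexpected event with actual or potential harm, including ill health | the Trust | Yes |
| 11 | concerns arising from monitoring | sponsor | Only if the Chief Investigator has such concerns |

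**Step 3: the one ambiguous line.** The 15-day sentence in 10.4 speaks of an event without repeating the word serious. It stands under a heading about SAEs, follows the paragraph on the SAE form and uses the HRA's SAE report form. Reading it as limited to SAEs is much the more natural.

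**Result.** Two routes are mandatory for this event: the record (10.3) and DATIX (10.8). No mandatory route leads to the R&I Office, REC or HRA. Section 10.5 does not help, since it only allows some SAEs to go unreported.

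**The case against.** The strongest reply is that the event is far from invisible. DATIX reporting under 10.8 is mandatory and depends on neither seriousness nor admission. An event that is unexpected and clearly harmful meets it. Section 10.6 reaches the REC, HRA and R&I Office within 3 days if urgent safety measures follow, and section 11 has the Chief Investigator take monitoring concerns to the sponsor. The study is at a single site, so the team that sees the event is also the team that decides whether to go on. The CRF would hold the event, and 10.2 requires its grades, so only the SAE count would omit it.

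All of this stands, and it rules out two stronger readings. A reader might infer that seriousness is the only trigger for any report, so that the event goes no further than the medical record and CRF. Section 10.8 contradicts that. A reader might also infer that the sponsor and REC could never learn of it. Sections 10.6 and 11 leave ways for them to do so, and the R&I Office appears to belong to the same Trust that receives DATIX reports.

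What the reply does not do is close the gap. Section 10.8 names neither the R&I Office, the REC nor the HRA as a recipient and makes no use of the causality grade. Sections 10.6 and 11 are conditional on a measure being taken or a concern arising.

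It is also fair to say that the five-criterion list is clear and consistently applied. This is a gap in coverage, not a contradiction.

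**Conclusion.** The point holds in a limited form. With the protocol followed exactly, a Severe, related and Unexpected event that is treated without admission and meets none of the five criteria has no required report to the R&I Office, REC or HRA. It must still be recorded in the medical records and CRF and reported to the Trust through DATIX.

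The conclusion rests on two assumptions: that the 15-day sentence in 10.4 covers SAEs only, and that some acute events at a one-day visit would be treated without admission and without being life-threatening or significantly disabling. The second is an inference from the visit design; the protocol neither describes such events nor gives their frequency. No rate can therefore be attached to the gap, and an interval around an assumed count would not measure it.

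Nor does the text support treating every Severe event as serious. Section 10.2 keeps severity and seriousness apart, and some Severe events are expected. This is an inexpensive improvement to safety oversight, not a flaw that threatens the study's conclusions.

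**What to change.** Add a sixth criterion to the SAE definition in section 10.1: *is otherwise considered medically significant by the investigator, including an event that needed treatment to prevent one of the outcomes above*. Events so classed then follow the existing 10.4 route: the form to the R&I Office and, when unexpected and related, the report to the REC and HRA. The reporting steps in 10.4 need no new rule, and the severity grades stay as they are.

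The cost is one line in 10.1 and at most a few additional SAE forms among 20 participants.
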